7.2 Adverse Events that are Potential Study Endpoint Events

Please note that AEs and SAEs that are listed below are being captured as events defined as endpoints for this clinical study (both efficacy and safety endpoints).

Symptomatic events that will be adjudicated include the following:

- Suspected symptomatic DVT
- Suspected symptomatic PE
- Suspected bleed
- Suspected stroke
- Death
- Suspected arterial thrombotic events (e.g., myocardial infarction, ischemic stroke, etc.)

Whenever the site becomes aware of one of these clinical events, it is crucial that the event is reported as soon as possible, preferably within 24 hours. These events must be reported following the rules as outlined for all adverse events in Section 7.1.

An appropriate event adjudication dossier will need to be submitted even if a suspected event is not confirmed by tests locally, for example if imaging did not confirm a new clinical event.

7.2.1 Reporting Requirements for AE's that are Potential Study Endpoints

The Study Site Manual for Venography and Event Reporting provides instruction for sites on the documentation, data collection, and reporting required for events considered (suspected) endpoints.

Typically for the above clinical events of suspected symptomatic DVT, suspected symptomatic PE, bleeding, stroke, or death, data will be collected in order to generate an adjudication dossier which will consist of eCRF data and supportive documentation which is assembled for review by the CIAC.

All suspected clinical outcomes must be reported as adverse events. Reporting a suspected outcome as an adverse event on the AE page in eCRF will automatically trigger an event specific form (refer also to eCRF completion guidelines). The eCRF triggered event forms contain a narrative section. In this narrative, a short clinical description should be provided: e.g. including symptom description and duration, eventually performed diagnostic tests or intervention with dates and description.

The supportive documentation (adjudication dossier) will depend on the type of clinical event and will typically consist of images and reports of the diagnostic tests done to explore the suspected clinical event, and other reports that could be relevant to the CIAC (e.g. medical records and/or hospital letters, discharge summaries, laboratory tests).

7.3 Monitoring of Subjects with Adverse Events

Any AE that occurs during the course of a clinical trial and is considered to be possibly related to the study drug must be monitored and followed up by the investigator until stabilization or until the outcome is known, unless the subject is documented as “lost to follow-up”. Reasonable attempts to obtain this information must be made and documented. It is also the responsibility of the investigator to ensure that any necessary additional therapeutic measures and follow-up procedures are performed. The sponsor will actively follow-up and collect information on any AE that occurs during the course of a clinical trial, however while this activity will continue for any serious AEs until stabilization or until the outcome is known, it will be discontinued at the time of database lock for non-serious AEs.

7.4 Treatment Interruption or Discontinuation

If an adverse reaction occurs during the administration of study drug, the infusion rate may be slowed or interrupted and the appropriate supportive measures instituted at the discretion of the physician. If the infusion is slowed, the total infusion time should not exceed two hours. Monitor the patient for at least one hour following completion of the infusion for signs or symptoms of an infusion reaction.

As with all protein products, administration of study drug may result in infusion reactions, including anaphylaxis or other hypersensitivity reactions. The infusion should be discontinued immediately if the patient experiences a serious infusion reaction such as signs of cardiovascular instability or respiratory compromise, and the appropriate supportive measures instituted. Patients should be evaluated and carefully monitored until complete resolution of signs and symptoms.

8.0 PATIENT WITHDRAWAL, REMOVAL OR SITE TERMINATION

8.1 Withdrawal or Removal of Patient From Study

Patients may withdraw from the study (withdraw consent) or be withdrawn by PI under the following circumstances:

- At their own request or at the request of their legally authorized representative;
- Patient is lost to follow-up;
- Investigator deems it necessary to stop study drug administration (e.g., for safety or for non-compliance to protocol); or
- At the specific request of the Sponsor.

In all cases, the reason for withdrawal must be recorded in the eCRF and in the patient's medical records. The patient must be evaluated to establish whether the reason was an AE, and, if so, this must be reported in accordance with the procedures outlined in Data Handling Procedures (see Section 9.0).

Even if the patient has decided to discontinue from the other study procedures, the Early Discontinuation Visit assessments should be performed approximately eight weeks after the patient's Day 1 (randomization) visit, if possible. In addition, those female patients required to use acceptable birth control during the study must be reminded that they should continue this form of birth control for a total of 10 weeks after receiving a dose of SelK2. The Investigator must make every effort to contact patients lost to follow-up on at least 2 occasions, including sending the patient a letter by certified mail (return receipt).

Occasionally patients may also withdraw consent to allow further data collection. Under such conditions, completion of the scheduled events, procedures, and assessments as specified in the protocol will not be possible. A record of the reason for discontinuation of data collection should be made on the appropriate eCRF page.

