3.4.2 Treatment Phase

After assessment that the patient has met all Inclusion Criteria and none of the Exclusion Criteria, on the day PRIOR to the scheduled TKA surgery, the patient will be randomized into this study. Prior to dosing of any study drug, baseline safety assessments will be taken.

For those randomized to receive SelK2, patients will receive a single dose of 7.5 mg/kg SelK2 via IV administration at least 12 hours prior to but not longer than 24 hours prior to the start of the TKA surgery. The Treatment Phase of the study consists of the period from the dosing of study drug (SelK2 or enoxaparin) or the TKA (for enoxaparin arm, if enoxaparin dosing is only done after TKA) up to the day of venography (Day 11 \pm 2) or early study termination. Note that for patients randomized to receive SelK2, study drug can be dosed either the day prior to TKA (Day 1) or on the day of TKA (Day 2) as long as the dosing occurs at least 12 hours prior to but not longer than 24 hours prior to the start of the TKA surgery.

For those randomized to receive enoxaparin, patients will receive 40 mg enoxaparin administered via SC injection 12 hours after TKA surgery followed by daily SC injections of 40 mg enoxaparin for at least 9 additional days post-surgery (with the option of giving an additional 40 mg enoxaparin SC dose 12 hours prior to TKA surgery).

For those randomized to receive SelK2 and enoxaparin, patients will receive a single dose of 7.5 mg/kg SelK2 via IV administration at least 12 hours prior to but not longer than 24 hours prior to

the start of the TKA surgery and will receive 40 mg enoxaparin administered via SC injection 12 hours after TKA surgery followed by daily SC injections of 40 mg enoxaparin for at least 9 additional days post-surgery.

For all patients, the Treatment Phase will be completed on the day the venography is completed.

Patients will remain in the hospital for AT LEAST two overnights after TKA. During the Treatment Phase, efficacy, safety and PK/PD/Immunogenicity assessments will be completed for each patient.

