3.4.3 Follow-Up Phase

After completion of the venography, each patient enters the Follow-Up Phase of the study which will last approximately 45 days. During this Phase, each patient will return for safety assessment on Day 21 and Day 57 (Final Study Visit). Patients will also be contacted on Day 29 and 43 by phone for assessment of any adverse events that have occurred since the last clinic visit.

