16. Anticipated use of intermittent pneumatic compression devices and/or electrical/mechanical muscle stimulators post TKA procedure;
17. Anticipated use of indwelling intrathecal or epidural catheters;
18. Participation in any other investigational study drug trial in which receipt of an investigational study drug occurred within 60 days prior to Day 1;
19. History of alcoholism or drug addiction within 1 year prior to Screening;
20. Any acute or chronic condition that, in the opinion of the Investigator, would limit the patient's ability to complete and/or participate in this clinical study; or
21. Unwillingness to comply with all study procedures including follow-up visits, as specified by this protocol, or unwillingness to cooperate fully with the Investigator.

* Birth control methods which are considered as highly effective are listed in the Clinical Trial Facilitation Group (CTFG) Guidance, Final Version – 2014-09-15.

One of these highly effective contraceptive methods must be used from the time of signing of the informed consent until 30 days after the Final Study Visit.

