6.4 Follow-Up Phase

The schedule of assessments and procedures to be performed during the Follow-up Phase are outlined below by Study Day and in the “Study Schedule of Events” (see Table 1).

6.4.1 Day 21

Patients will undergo the following procedures on Day 21.

1. Abbreviated physical examination;
2. Vital signs including sitting blood pressure, pulse rate, respiratory, and temperature after sitting for 3-5 minutes;
3. Collection of clinical laboratory samples (blood and urine) to be shipped to the central lab for evaluation of hematology, blood chemistry, coagulation parameters and urinalysis;
4. Collection of blood samples for hsCRP and D-dimer assessments;
5. For patients randomized to the SelK2 arm or SelK2 + enoxaparin arm, collection of blood samples for PK, PD, and immunogenicity assessments;
6. Record concomitant medications and transfusion; and
7. Assessment of AEs.

6.4.2 Day 29

Phone contact to assess the following:

1. Record concomitant medications and transfusions; and
2. Assessment of AEs.

6.4.3 Day 43

Phone contact to assess the following:

1. Record concomitant medications and transfusions; and
2. Assessment of AEs.

6.4.4 Day 57

Patients will undergo the following procedures on Day 57.

1. Complete physical examination;
2. 12-lead ECG;
3. Vital signs including sitting blood pressure, pulse rate, respiratory, and temperature after sitting for 3-5 minutes;
4. Collection of clinical laboratory samples (blood and urine) to be shipped to the central lab for evaluation of hematology, blood chemistry, coagulation parameters and urinalysis;
5. Collection of blood samples for hsCRP and D-dimer assessments;

6. For patients randomized to the SelK2 arm or SelK2 + enoxaparin arm, collection of blood samples for PK, PD, and immunogenicity assessments;
7. Record concomitant medications and transfusions; and
8. Assessment of AEs.

The completion of assessments listed above on Day 57 marks the completion of each patient in this study.

Patients should be reminded that they must remain on a highly effective contraceptive method until 30 days after their Final Study Visit.

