7.1 Procedures for Handling and Reporting Adverse Events

7.1.1 Adverse Event

An **adverse event** (AE) is any undesirable medical event affecting a patient during a clinical trial. An AE can therefore be defined as any sign, symptom, syndrome, or new illness that appears while a patient is participating in this clinical study (from Randomization to final study visit (either Day 57 Visit or Early Discontinuation Visit)) or, if present at baseline, worsens in a patient during the period of observation in the clinical study and that may impair the well-being of the patient. The term also covers laboratory findings or results of other diagnostic procedures that are considered to be medically important (e.g., that require unscheduled diagnostic procedures, treatment measures, or result in withdrawal from the study). An AE may or may not have a causal relationship with the study drug. The period of observation for AEs is defined as from the point at which the patient is randomized into the study to the completion of the Follow-Up Phase assessments at Day 57 (or the Early Discontinuation Visit, if patient early discontinues).

An AE may be:

- A new illness;
- Worsening of a sign or symptom of the condition under treatment or of a concomitant illness;
- An effect of the study drug;
- Unrelated to participation in the clinical study; or
- A combination of one or more of these factors.

Surgical procedures themselves are not AEs; they are therapeutic measures for conditions that require surgery. However, the condition for which the surgery is required may be an AE. Planned surgical measures permitted by the study protocol and the condition(s) leading to these measures are not AEs.

Each AE is to be recorded only once on the “Adverse Event” eCRF page with *seriousness* and maximum *intensity* that occurred over the duration of the event. Each event also should be evaluated with respect to *causality* and *actions taken*. All AEs are to be monitored and recorded from the point of study Randomization through Day 57 (or earlier if patient discontinues from the study). For all AEs that require the patient to be discontinued from the study, the event(s) will be followed until final resolution or stabilization of the event(s). Note that unexpected SAEs should be reported as outlined in Section 7.1.2. Adverse events may be identified by spontaneous patient report or from standardized open-ended verbal probes.

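### Women who receive SelK2 and then withdraw are given two incompatible end dates for contraception, 16 days apart on the protocol's own schedule

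*Combined protocol and SAP*

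**What the plan says.** Three places in the combined protocol and SAP set an end to contraception.

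- **Section 4.2, closing footnote.** It belongs to the female and male contraception criteria in Section 4.1. A highly effective method "must be used from the time of signing of the informed consent until 30 days after the Final Study Visit". It names no treatment arm and makes no exception for patients who withdraw.
- **Section 6.4.4 (Day 57).** Patients completing the study are reminded that "they must remain on a highly effective contraceptive method until 30 days after their Final Study Visit".
- **Section 8.1 (withdrawal or removal).** Female patients are to be reminded that "they should continue this form of birth control for a total of 10 weeks after receiving a dose of SelK2".

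Three further passages fix the timing. Section 3.4.3 puts the last visit at Day 57: "each patient will return for safety assessment on Day 21 and Day 57 (Final Study Visit". Section 8.1 says of patients who leave early that "the Early Discontinuation Visit assessments should be performed approximately eight weeks after the patient's Day 1 (randomization) visit, if possible". Section 7.1.1, in defining the adverse event period, refers to the "final study visit (either Day 57 Visit or Early Discontinuation Visit", and Table 1 puts both visits in one column with a window of ±2 days. On dosing, Section 3.4.2 notes that "study drug can be dosed either the day prior to TKA (Day 1) or on the day of TKA (Day 2".

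The listing of protocol modifications does not touch the contraception period, so all of this is current text.

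**The concern.** The Section 4.2 footnote counts from a visit and Section 8.1 counts from a dose. Both apply to a woman who must use contraception, has received SelK2 and withdraws. A site following the text as written has two end dates for her and nothing to say which prevails.

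This is a patient-safety instruction after a single dose of a monoclonal antibody, and it concerns patients whom the site may find hard to contact again. The Early Discontinuation Visit list in Section 6.4.5 has no contraception reminder, unlike the Day 57 list in Section 6.4.4. Section 8.1 is therefore the only reminder written for early leavers, and it is the one that departs from the eligibility rule.

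**Working it through.** This is calendar arithmetic; no sample-size or error-rate formula is involved.

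**Inputs**
- Final visit: Day 57, ±2 days (Section 3.4.3, Table 1).
- Early Discontinuation Visit: about eight weeks after Day 1 (Section 8.1).
- SelK2 dose: Day 1 or Day 2 (Section 3.4.2).
- Rule A (Section 4.2 footnote): end day = final visit day + 30.
- Rule B (Section 8.1): end day = SelK2 dose day + 70, since 10 weeks × 7 = 70 days.

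**Step 1. Check the visit timing.** (57 − 1) / 7 = 8.0 weeks. The eight-week visit in Section 8.1 is the nominal Day 57 visit, so the schedule is consistent on this point.

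**Step 2. Does the 10-week figure follow from Rule A?** With a Day 57 visit, Rule A ends on 57 + 30 = Day 87. That is 86 days, or 86 / 7 = 12.3 weeks, after a Day 1 dose. It is not 10 weeks.

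**Step 3. Compare the rules at the scheduled visit.**

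| Final visit | Rule A ends | Rule B ends, Day 1 dose | Rule B ends, Day 2 dose | A minus B |
|---|---|---|---|---|
| Day 55 | Day 85 | Day 71 | Day 72 | 14 or 13 days |
| Day 57 | Day 87 | Day 71 | Day 72 | 16 or 15 days |
| Day 59 | Day 89 | Day 71 | Day 72 | 18 or 17 days |

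The nominal gap is 87 − 71 = 16 days. The extremes are 85 − 72 = 13 and 89 − 71 = 18. No permitted combination of visit and dosing day makes the rules agree.

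**Step 4. Where would they agree?** Set final visit + 30 = dose day + 70. The final visit would have to be on Day 41 (Day 1 dose) or Day 42 (Day 2 dose).

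**Step 5. Earlier visits (assumed dates, Day 1 dose).** A last visit on Day 43 ends Rule A on Day 73, 2 days after Rule B. A last visit on Day 21 ends Rule A on Day 51, 20 days before Rule B. The order reverses below about Day 41.

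**Step 6. Compare the populations.** The Section 4.2 footnote covers both sexes and all arms. Section 8.1 names only female patients and counts from SelK2. For withdrawn men, and for patients who received only enoxaparin, it is silent.

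**The case against.** The best defence is that the 10-week rule is a deliberate fallback for patients who may never attend a final visit. A count from the dose would then make sense. But the text does not say this, the Section 4.2 footnote has no carve-out, and Section 8.1 itself asks for a visit at about eight weeks, where both rules can be computed and disagree.

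Four stronger readings are tempting, and the documents do not support them.

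- *A contradiction across the whole trial.* Section 6.4.4 addresses patients at Day 57, and for completers it agrees with the Section 4.2 footnote. Section 8.1 addresses withdrawal. The clash is between the Section 4.2 footnote and Section 8.1, for withdrawn women who received SelK2.
- *A second, weaker standard of method.* Section 8.1 uses the word acceptable where Section 4.2 requires highly effective methods. But it tells women to continue the form already required of them during the study. This is loose wording and does not clearly set a lower standard.
- *A gap that routinely changes direction.* Reversal needs a last visit well ahead of the schedule. Section 8.1 qualifies its timing with if possible, so this can happen, but it is not the planned case. It also disappears if Final Study Visit means Day 57 only, as Section 3.4.3 could be read; the 16-day gap then remains.
- *One of the periods is unsafe.* The toxicology, disposition, clinical experience and dose rationale text is not available, so neither period can be judged.

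It also stands that the affected group cannot be sized. Postmenopausal women are outside the requirement, and the documents give neither a withdrawal rate nor the number of women of child-bearing potential. The 20% in Section 10.1 concerns non-evaluable endpoint data, which is a different quantity.

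**Conclusion.** The concern holds for women required to use contraception who receive SelK2 and then withdraw. At the eight-week visit that Section 8.1 schedules, the two rules end at about Day 87 and Day 71: 16 days apart, and 13 to 18 across the ±2-day window and both dosing days. This rests on taking the Section 4.2 footnote as written, without an exception for withdrawal, and on the Early Discontinuation Visit counting as a final study visit.

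The silence of Section 8.1 on withdrawn men and on enoxaparin-only patients is a gap in the reminder and does not contradict Section 4.2. A reader might infer that completers and early leavers must share one rule. That is a clinical choice; two clearly separated rules would also remove the conflict. Neither period is endorsed here.

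**What to change.** The sponsor should reconcile Section 8.1 with the Section 4.2 footnote and keep Section 6.4.4 consistent with the result. The revised text should state explicitly:

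- which end point applies to patients who withdraw, including those who attend no final visit;
- which patients it covers, so that men and patients who received only enoxaparin are addressed;
- that the method is the one already required during the study, if that is what is meant.

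A matching reminder in Section 6.4.5 would put the instruction in the visit list that sites use. The sponsor decides the period and whether it differs between completers and early leavers.

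The cost is protocol wording and matching patient information. Sample size, error rates and the analysis do not change.

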8.2 Termination of Study

The study may be terminated at any time for the following reasons: 1) Investigator/IRB/EC at a specific site after consultation with the Sponsor stops study for safety reasons; 2) Sponsor may also stop the study at one or more sites due to safety, site noncompliance, loss or lack of data quality, or project termination; 3) if the governing Regulatory Agency mandates study stop; or 4) for safety if recommended by the Steering Committee with Sponsor agreement. If the study is stopped at a site due to the action of the Investigator/IRB/EC, IQVIA and the Sponsor should be informed immediately. See Section 12.8 for further instructions on premature closure of the study.

9.0 DATA HANDLING PROCEDURES

9.1 Electronic Case Report Form Completion

Access to the eCRF will be granted to Investigator and/or delegated staff after completion of proper training. Data from source documents will be entered directly onto the eCRF by the Investigator or designated representative. The eCRF must be reviewed by the Investigator. The eCRF should be kept current to allow the clinical monitor to be able to review the patient's current status. Once the patient has completed the study and all data have been entered onto the eCRF, the eCRFs will be electronically signed by the Investigator.

9.2 Database Construction

Missing data and inconsistencies will be identified through an extensive computerized editing procedure. The accuracy of the clinical database will be verified through a series of reviews of data listings and other pertinent data processing reports. As a final quality control measure, the database will be proofread and the data listings will be reviewed to ensure that they are understandable, complete, and reliable.

10.0 STATISTICAL METHODS AND PLANNED ANALYSES

10.1 Sample Size and Power

Assuming that the rate of VTE for the active comparator (enoxaparin) arm of this study will be 25%, it is estimated that a sample size of 76 evaluable patients per arm should give the study 80% power of declaring non-inferiority between the SelK2 arm and the enoxaparin active comparator arm. This calculation uses a one-sided 90% CI with a non-inferiority margin of 15%. This calculation assumes that the underlying rate of VTE for the SelK2 and enoxaparin arms will be identical at 25% and with the non-inferiority margin set as at the midpoint between the expected active therapy response compared to an assumed placebo event rate in this patient population of 55%. Consequently, making the conservative estimate that up to 20% of randomized patients may not yield evaluable endpoint data, a total of 95 patients will be enrolled per arm to provide at least 76 endpoint evaluable patients per arm.

Sample Size Considerations for Adaptive Arm:

With the same assumptions as above the for active comparator (enoxaparin) arm of the study event rate, it is estimated that a sample size of 76 evaluable patients in a combination therapy arm of SelK2 and enoxaparin should give the study 80% power of declaring superiority between the SelK2 and enoxaparin arm and the enoxaparin active comparator arm for an estimated SelK2 and enoxaparin VTE event rate of 6% (an 19% difference between combination treatment effect and active comparator treatment effect). This calculation assumes a two-sided 0.1 alpha, a Pearson Chi-squared test, and a superiority comparison.

